**Table 6-8 Efficacy Analysis Visit Definitions for MSQ v2.1**

Analysis Visit (Derived)	Scheduled Visit Day a	Window
Baseline	Visit 1 (Enrollment)	Baseline from lead-in study
Week 4	Day 28 (Visit 2)	Treatment Day [1, 42]
Week 8	Day 56 (Visit 3)	Treatment Day [43, 70]
Week 12	Day 84 (Visit 4/ET)	Treatment Day $\geq 71$ and within the open-label treatment period
Week 16 (Follow-up)	Day 112 (Visit 5)	Treatment Day [end of the open-label treatment period +1, the last study visit]

ET = early termination.

a Relative to the date of the first dose of open-label study treatment.

The analysis visit windows for safety endpoints are defined as follows:

**Table 6-9 Safety Analysis Visit Definitions**

Analysis Visit (Derived)	Scheduled Visit Day a	Window
Baseline		Baseline from lead-in study
Week 4	Day 28 (Visit 2)	Treatment Day [1, 42]
Week 8	Day 56 (Visit 3)	Treatment Day [43, 70]
Week 12	Day 84 (Visit 4)	Treatment Day $\geq 71$ and within the open-label treatment period
End of the Open-label treatment Period		Last available assessment during the open-label treatment period
Week 16 (Follow-up)	Day 112 (Visit 5)	Treatment Day [end of the open-label treatment period +1, the last study visit]
End of study		Last available assessment after treatment start date, i.e. occurs at final visit (expected Day 112) or ET

a Relative to the date of the first dose of open-label study intervention.

End of Treatment is defined as the last available assessment during open-label treatment period, i.e. on or before the treatment end date. End of Treatment results will be presented in summary tables for clinical laboratory values, electrocardiogram and vital signs.

End of Study is defined as the last available assessment during the study, including open-label and safety follow-up period.

End of Study results will be presented in summary tables for safety parameters, including but not limited to clinical laboratory values, and vital signs (not for electrocardiograms, as these data were not collected during follow-up period).

ET = early termination. EOS=end of study.

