5.6 Treatment Regimen and Dosing

Participants who meet all of the study entry criteria at Visit 1 will be treated with atogepant 60 mg once daily.

Participants will be provided with atogepant to be taken on an outpatient basis.

Participants will be instructed to take their atogepant at approximately the same time each day. Atogepant will be administered orally for 12 weeks, and participants will be followed for 4 weeks following completion or discontinuation of the atogepant.

Table 5-1. Study Intervention

Drug/Dose	Study Intervention Frequency	Route of Administration
Atogepant 60 mg	Once daily	Oral

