8.4.1 Open-label Treatment Period (12 Weeks)

8.4.1.1 Visit 1 (Day 1)

- Obtain informed consent and participant privacy.
- Register participant in IWRS.
- Collect medical history for participants who have a gap between the last visit of the lead-in study and Visit 1 of this extension study.
- Collect start date (first day) of last menstrual cycle for women having menstrual cycles.
- Review and update concomitant medications and concurrent procedures.
- Perform urine pregnancy test for women of childbearing potential.
- Perform and transmit ECG.
- Collect vital sign measurements (sitting and standing systolic and diastolic BP, sitting and standing pulse rate, respiration rate, temperature, and weight).
- Assess C-SSRS (the “Since Last Visit” assessment of the C-SSRS will be completed).
- Assess inclusion/exclusion criteria.

If the participant continues to meet study entry criteria, including acceptable results from Visit 1 ECG, pregnancy test, and vital sign measurements (see Section [6.1](#)) the following procedures will be carried out at Visit 1.

- Prior to any other test or evaluations, administer the MSQ v2.1.
- Perform physical examination.
- Collect blood and urine for clinical laboratory determinations including: chemistry, hematology, serology, INR, and urinalysis.
- Collect urine for drug screen.
- Review and assess AEs.
- Provide eDiary instructions and training
- Access IWRS and obtain the kit number for atogepant bottle and dispense atogepant bottle.

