8.4.1.2 Visits 2 and 3 (Week 4 and Week 8)

- Review clinical laboratory results from Visit 1 to confirm continued eligibility (Visit 2 only) (see Section 8.9).
- Prior to any other test or evaluations, administer the MSQ v2.1.
- Perform urine pregnancy test for women of childbearing potential.
- Collect vital sign measurements (sitting and standing systolic and diastolic BP, sitting and standing pulse rate, respiration rate, temperature, and weight).
- Collect start date (first day) of last menstrual cycle for women having menstrual cycles.
- Collect blood and urine samples for chemistry, hematology, INR, and urinalysis.
- Assess C-SSRS (the “Since Last Visit” assessment of the C-SSRS will be completed).
- Perform and transmit ECG (Visit 3 only).
- Collect previous visit atogepant bottle, review participant compliance, and perform accountability.
- Review and assess AEs.
- Review and update concomitant medications/concurrent procedures.

- Review eDiary data and compliance
- Access IWRS to dispense atogepant bottle and enter accountability.

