### 1.2. Study Design

This is a multicenter, open-label, 12-week, safety extension study conducted in China. Participants will be treated with atogepant 60 mg once daily, to be taken on an outpatient basis at approximately 2 centers.

The study will consist of a 12-week treatment period and a 4-week safety follow up period. All participants who complete Study 3101-303-002, and meet all eligibility requirements may participate in this study.

After signing the informed consent, Chinese participants will directly rollover from Study 3101303-002 (Phase 3 CM); hereafter referred to as the lead-in study. As such, participants will have Visit 7 from the lead-in study function as Visit 1 for this extension study (3101-311-002). After Visit 1, study visits will occur every 4 weeks during the 12-week open-label treatment period. A safety follow-up visit will occur 4 weeks after the last dose of atogepant 60 mg in the open-label treatment period.

Note, there may be participants who complete Visit 7 in the lead-in study before this extension study (3101-311-002) has been initiated. Those participants should complete Visit 7/ET and Visit 8/end of study (EOS) Visit (including discontinuation of study intervention) per the lead-in study Schedule of Visits and Procedures.

Depending on the timing of the initiation of this extension study (3101-311-002), in relation to each participant's planned Visit 8 schedule in the lead-in study, Visit 1 for this extension study can be conducted on the same day as Visit 8/EOS Visit for the lead-in study, or soon thereafter.

- If this extension study is initiated prior to the participant's planned Visit 8 in the lead-in study, then Visit 8/EOS Visit in the lead-in study should be conducted on the same day as Visit 1 for this extension study (3101-311-002).
- If this extension study is not initiated prior to the participant's planned Visit 8 in the lead-in study (ie, there is a gap between Visit 8 of the lead-in study and Visit 1 of this extension study), then Visit 8/EOS should be conducted as planned per the lead-in study Schedule of Visits and Procedures. When this extension study is initiated, the participant should return to the clinic as soon as possible, and Visit 1 for this extension study should be conducted per [Table 1-1 Schedule of Visits and Procedures](#).

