### 6.4. Data handling convention

Day 1 is defined as day for the date of the first dose of open-label study intervention. There is no Day 0 or Week 0. Treatment day is relative to the date of the first dose of open-label study intervention.

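### SAP Tables 6-8 and 6-9 can class a Visit 1 record taken before open-label dosing as Week 4, and for ECG it is the only scheduled record in that window

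*SAP*

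**What the plan says.** SAP 6.4 counts treatment days from the first open-label dose: "Day 1 is defined as day for the date of the first dose of open-label study intervention". It allows no Day 0 and does not split Day 1 by time.

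SAP Table 6-9 (safety) and Table 6-8 (MSQ) both define Week 4 as "Treatment Day [1, 42", closed at both ends, and link it to Visit 2 on Day 28. Table 6-9 has no row for Visit 1. In Table 6-8 the Baseline row carries the scheduled-visit label "Visit 1 (Enrollment" (bracket closed in the original), but its window is the lead-in baseline. SAP 5.1 agrees with the window: for clinic-visit endpoints, baseline is the last value before the first lead-in dose.

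Protocol 8.4.1.1 schedules Visit 1 as Day 1. Entry to the second half of that visit depends on the participant meeting the criteria, "including acceptable results from Visit 1 ECG, pregnancy test, and vital sign measurements". MSQ is to be given before other tests, and dispensing is the last listed step. At Visits 2 and 3 the ECG instruction is "Perform and transmit ECG (Visit 3 only" (bracket closed in the original), so Visit 2 has none.

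For direct rollovers, SAP 1.2 says that "participants will have Visit 7 from the lead-in study function as Visit 1 for this extension study". The same section also describes a lead-in Visit 8 held on the same day as Visit 1, and a Visit 1 held after a gap.

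**The concern.** A value labelled Week 4 should describe about four weeks of open-label atogepant. A Visit 1 value describes the end of lead-in treatment, or the time off treatment after it. The MSQ recalls four weeks, so a Visit 1 MSQ covers no open-label treatment at all.

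Safety is the primary objective. If the derived visit is printed or used, an eligibility ECG would appear as on-treatment evidence. For the other measures, two programmers could reasonably choose different records as the Week 4 value. Similarly, a Visit 1 value could become End of Treatment for a participant who stops early.

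**Working it through.** **Inputs.** Visit 1 is Day 1. Visits 2 to 5 are Days 28, 56, 84 and 112, each ±3 days (Protocol Table 1; SAP Table 1-1). ECGs are scheduled at Visits 1, 3 and 4. Laboratory tests, vital signs and MSQ are scheduled at Visits 1 to 5. Windows are from SAP Tables 6-8 and 6-9.

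**1. The plan's window limits.** The upper limits reproduce as midpoints between scheduled visits: (28 + 56)/2 = 42 for Week 4 and (56 + 84)/2 = 70 for Week 8. The lower limit of Week 4 is not a midpoint, since (1 + 28)/2 = 14.5. The window simply starts on the first treatment day, and so takes in the Visit 1 day.

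**2. Where scheduled records fall if the first dose is on the Visit 1 date.**

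| Visit | Days allowed | Derived visit | ECG | Labs, vital signs, MSQ |
|---|---|---|---|---|
| 1 | 1 | Week 4 | yes | yes |
| 2 | 25–31 | Week 4 | no | yes |
| 3 | 53–59 | Week 8 | yes | yes |
| 4 | 81–87 | Week 12, if within the treatment period | yes | yes |
| 5 | 109–115 | Week 16 | no | yes |

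Per participant, Days 1 to 42 hold one scheduled ECG (Visit 1) and two scheduled records for each other measure (Visits 1 and 2). If Visit 2 is remote, Protocol Table 12-1 includes no laboratory tests or vital signs, so Visit 1 could be the only scheduled Week 4 record for those too.

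**3. Selection rule.** SAP 6.4.4 says which of several repeated values becomes the end-of-study value. It does not address two records in one visit window. SAP 6.4.2.1 does give such a rule for duplicate diary records.

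**4. If the first dose is later than Visit 1.** A record from the day before the first dose is Day −1, as there is no Day 0. It falls in no weekly window, and it cannot be baseline under SAP 5.1. So Visit 1 has no proper place on either dosing date. The documents do not fix that date: "Participants will be provided with atogepant to be taken on an outpatient basis".

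**5. Who has a Visit 1 record in this study.** SAP 1.2 gives three entry routes.
- *Gap after lead-in Visit 8:* Visit 1 is run on this study's own schedule, so the record is held here.
- *Lead-in Visit 7 serving as Visit 1:* footnote a of Table 1-1 says that Visit 7 procedures are not repeated. Whether the lead-in records are carried over is not stated.
- *Lead-in Visit 8 on the same day as Visit 1:* the no-repeat instruction names only Visit 7, and the source of the record is again not stated.

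**6. End-of-period values.** The Table 6-9 note takes End of Treatment as the last assessment in the open-label period, on or before the treatment end date. It sets no lower limit, and the protocol lists Visit 1 under "8.4.1 Open-label Treatment Period (12 Weeks" (bracket closed in the original). A Visit 1 value could therefore serve, but only for an early stopper with no later on-treatment assessment. For End of Study, the table row requires an assessment after treatment start, whereas the note beneath it has no such limit.

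**The case against.** The strongest reply is that little in the current plan uses these windows. SAP 5.1 and 5.4.4 list the safety data, SAP 5.3.4 lists MSQ, and SAP 6.2 removes the laboratory, vital-sign and ECG summaries. SAP 6.4.4 keeps every assessment in the listings, so no record is lost. Listing layouts are in a separate document (SAP 1), so it is not known whether the derived visit is printed. This largely stands and is why the point is minor. It is not a full answer, because the notes to Table 6-9 still send End of Treatment and End of Study results to summary tables.

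A second reply is that both tables tie Week 4 to Visit 2 on Day 28, so the intent is clear. The intent is clear, but the scheduled-visit column is not an exclusion rule. Assignment follows the day window.

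A third is that misclassification needs two conditions: a first dose on the Visit 1 date, and a Visit 1 record held in this study. That stands, and the finding is limited to such records.

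A fourth concerns early stoppers. Visit 4/ET sits under the same protocol heading as Visit 1, and Protocol 8.8 asks for those assessments after early discontinuation. If an ET assessment counts as within the treatment period, it displaces Visit 1. The date clause in the Table 6-9 note cuts the other way when ET follows the last dose. The End of Treatment point is therefore narrow.

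**Conclusion.** The window rule is wrong as written, and the consequence is minor. When a Visit 1 record is held in this study and the first dose is on the same date, a pre-dose record is classed as Week 4. It is the only scheduled Week 4 ECG, and one of two scheduled records for laboratory tests, vital signs and MSQ. With about 3 participants expected (SAP 3) and output mainly in listings, the likely effect is a wrong visit label.

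A reader might infer more than the documents support:
- *That every participant is affected.* The dosing date and the handling of lead-in Visit 7 and Visit 8 records are not stated, so the number affected cannot be given.
- *That neither table mentions Visit 1.* Table 6-8 does name it, in a Baseline row whose window contradicts the label. The plain absence is in Table 6-9.
- *That End of Treatment values will generally predate dosing.* This can arise only for the early stoppers described above, and no early-stop rate is given.
- *That safety signals would be missed.* PCS determination uses all assessments after the lead-in baseline (SAP 6.4.4), whatever the window label.

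**What to change.** 1. Add a row for Visit 1 / pre-open-label to Tables 6-8 and 6-9. Assign scheduled Visit 1 records to it by nominal visit, including any lead-in Visit 7 or Visit 8 records that serve as Visit 1. State whether those lead-in records enter this study's data.
2. Leave the Week 4 day limits unchanged for all other records. Starting the window on Day 2 is unnecessary, and would leave an unscheduled post-dose assessment on Day 1 without an analysis visit.
3. State that pre-open-label Visit 1 records cannot supply the Week 4, End of Treatment or End of Study values. Align the End of Study note with its table row.
4. Correct the Table 6-8 Baseline label so that it refers to the lead-in baseline.

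PCS determination stays as planned. The Week 4 ECG row will then hold only unscheduled or early-termination ECGs, which matches the schedule. The cost is SAP wording and one nominal-visit condition in the programs. No dose times or other new data are needed.

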6.5 Summary of Methods of Data Collection

An IWRS will be used to manage atogepant inventory. All office visit data for this study will be collected by either the eTablet (eg, C-SSRS) or eCRFs via an electronic data capture system. Source documents will be used at the sites and may include a participant’s medical record, hospital charts, clinic charts, the investigator’s participant study files, as well as the results of diagnostic tests such as laboratory tests, ECGs, etc. A centralized clinical laboratory will be used for the analysis of all blood and urine samples, and for ECG assessments. Additional information on the collection and handling of samples is detailed in the Laboratory Procedure Manual.

All participants will use an eDiary daily to record the daily total duration of headache, headache characteristics, associated symptoms, the worst pain severity, acute medication use, AIM-D, Activity Level, and Activity Limitation during the open-label treatment period until Visit 4. Training for the eDiary will be provided for qualified participants during Visit 1.

7 Statistical Procedures

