## 6.2. Appendix 2: Changes to Protocol-Planned Analyses

The following changes to the Protocol amendment 1 were made in this SAP:

1. Section 7.2.2 of the protocol amendment 1 stated that “The related health outcome analyses will be documented in the health economics and outcomes research statistical analysis plan.” Instead, these health outcome analyses are added to this SAP document.
2. Removed following efficacy variables:
  - Change from baseline in monthly headache days at each monthly period.
  - Change from baseline in monthly acute medication use days at each monthly period.
  - $\geq 25\%$ ,  $\geq 50\%$ ,  $\geq 75\%$ , and 100% improvement (decrease) in monthly migraine days at each monthly period.
  - Change from baseline in monthly cumulative headache hours at each monthly period
  - Change from baseline in monthly triptan use days at each monthly period
  - Change from baseline in monthly moderate/severe headache days at each monthly period
  - Change from baseline in monthly severe headache days at each monthly period.
  - Other Health Outcome endpoints (see Section 5.3.1)
3. Efficacy variables will be listed, and will not be summarized.
4. Removed following demographic table summaries. Where noted in the body of the SAP, data will be presented in listings:
  - Analysis populations
  - Summary of enrollment category
  - Concomitant medication during the follow-up period
5. Removed following safety summaries. Where noted in the body of the SAP, data will be presented in listings:
  - TEAEs by SOC, PT and severity
  - NEAEs
  - Common ( $\geq 2\%$ ) TEAEs by PT
  - Summary of baseline, post-baseline, and change from baseline in laboratory parameters
  - Summary of baseline, post-baseline, and change from baseline in vital signs
  - Summary of baseline, post-baseline, and change from baseline in ECG

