#### **6.4.4. Repeated or Unscheduled Assessments of Safety Parameters**

Baseline is defined as the last assessment made before the first dose of double-blind study treatment in the lead-in study. If end-of-study assessments are repeated or if unscheduled visits occur, the last nonmissing postbaseline assessment will be used as the end-of-study assessment for generating summary statistics. However, all postbaseline assessments will be used for PCS value determinations, and all assessments will be presented in the data listings.

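### Do the SAP visit windows mislabel a Visit 4 held after the last dose, or give early off-drug visits two labels, in a way that matters?

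*SAP*

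**What the plan says.** SAP Tables 6-8 (MSQ v2.1) and 6-9 (safety) use the same windows. Week 4 is Days 1 to 42 and Week 8 is Days 43 to 70, neither with an on-treatment condition. Week 12 is Day 71 or later, provided the record lies inside the open-label period. Week 16 (Follow-up) is "Treatment Day [end of the open-label treatment period +1, the last study visit", with no minimum day. SAP 6.4 adds that "Treatment day is relative to the date of the first dose of open-label study intervention", so the count continues after dosing stops.

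The nearest thing to a definition of the period's end is the note under Table 6-9: "End of Treatment is defined as the last available assessment during open-label treatment period, i.e. on or before the treatment end date". The SAP does not define treatment end date.

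Other text treats Visit 4 as part of the open-label period:

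- Both schedules (Protocol Table 1, SAP Table 1-1) place Visit 4 in the open-label columns.
- Protocol 6.5 has the eDiary kept "during the open-label treatment period until Visit 4".
- Table 6-8 maps Visit 4/ET to Week 12.
- The Table 6-9 note excludes ECGs from End of Study tables ("not for electrocardiograms, as these data were not collected during follow-up period"), yet an ECG is scheduled at Visit 4.

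On output, the Table 6-9 note says "End of Treatment results will be presented in summary tables for clinical laboratory values, electrocardiogram and vital signs". SAP 6.2 removes "Summary of baseline, post-baseline, and change from baseline in laboratory parameters" and the matching vital-sign and ECG summaries. SAP 6.4.4 states that "all postbaseline assessments will be used for PCS value determinations, and all assessments will be presented in the data listings".

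**The concern.** Two things look wrong. First, if the open-label period ends at the last dose, a Visit 4 held a day or more after it fails the Week 12 condition and becomes Week 16. Week 12 is then empty, Visits 4 and 5 share a label with no rule for choosing between two MSQ records, and End of Treatment falls back to Visit 3, about Day 56 for a completer. Protocol 8.4.1.3 asks sites not to hold Visit 4 before 12 weeks have passed, which pushes visits to the late side.

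Second, for a participant who stops early, a record taken off drug before Day 71 meets the Week 4 or Week 8 window and the Week 16 window together. A value about four weeks after the last dose could then appear under Week 4 or Week 8. In a study meant to describe safety on treatment, blurring on-drug and off-drug values would matter if the outputs were built on these labels.

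**Working it through.** **Rules as written.** Let d be the treatment day of the visit, L the day of last dose and E the last day of the open-label period.

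- Week 4: 1 ≤ d ≤ 42
- Week 8: 43 ≤ d ≤ 70
- Week 12: d ≥ 71 and d ≤ E
- Week 16: d ≥ E + 1

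The cut-offs are midpoints between scheduled visits: (28 + 56)/2 = 42 and (56 + 84)/2 = 70.

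**Reading A: E = L.** Visit 4 is due on Day 84 ± 3, so d runs from 81 to 87. The documents do not fix L relative to the visit, so three patterns are assumed:

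| Last dose | Week 12 | Week 16 |
|---|---|---|
| On the visit day | 7 of 7 days | 0 of 7 |
| On the visit day, but no later than Day 84 | Days 81–84 (4 of 7) | Days 85–87 (3 of 7) |
| The day before the visit | 0 of 7 | 7 of 7 days |

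These are possible outcomes under each assumption and do not estimate a mislabelling rate.

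For an early stop with L = 20 and the ET visit on Day 22: 22 ≤ 42 gives Week 4, and 22 ≥ 21 gives Week 16. Visit 5 falls on Day 20 + 28 = 48, which gives Week 8 and also Week 16. Under this reading every post-dose day before Day 71 has exactly two labels, and every post-dose day from Day 71 on has Week 16 only.

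**Reading B: E = day of Visit 4/ET.** A Visit 4 on Day 85 after a last dose on Day 84 is Week 12. The Day 22 ET visit is Week 4 only. Visit 5 on Day 48 is still Week 8 and Week 16.

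**What survives both readings.** A Visit 5 on or before Day 70 has two labels. With Visit 5 at L + 28, L + 28 ≤ 70 gives L ≤ 42: Week 4 and 16 for L = 1 to 14, Week 8 and 16 for L = 15 to 42. With the ± 3-day window, overlap is certain when L + 31 ≤ 70 (L ≤ 39) and possible when L + 25 ≤ 70 (L ≤ 45).

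**Which outputs use these labels?**

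| Output | Basis | Affected? |
|---|---|---|
| Monthly migraine days (SAP 5.3.1, Table 6-7) | Fixed Days 1–28, 29–56, 57–84 | No |
| Treatment-emergent AEs (SAP 5.4.3) | Onset dates against dose dates and Visit 5 | No |
| Potentially clinically significant values (SAP 6.4.4) | All post-baseline records | No |
| Laboratory, vital signs, ECG (SAP 5.4.4) | Listings of each assessment | Label only |
| MSQ (SAP 5.3.4, 6.2) | Listing | Label only |
| C-SSRS (SAP 5.4.4.4) | Listing of participants with any finding | No |
| End of Study (SAP 6.4.4) | Last non-missing record | No |
| End of Treatment tables (Table 6-9 note) | Labels | Only if produced, against SAP 6.2 |

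Only the last row could carry a wrong label into a summary. It rests on sentences left from the plan for about 120 participants; the current SAP expects about 3.

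**The case for a change.** The strongest reply is that small numbers bear on how serious a defect is and leave it a defect all the same: with 3 participants, one mislabelled visit is a third of what is shown for that time point. The overlap is also not far-fetched. Protocol 8.9 withdraws participants on Visit 1 laboratory, drug-screen or serology results, and Protocol 8.4.1.2 has the Visit 1 laboratory results reviewed at Visit 2, after dosing has begun. If such a participant's last dose is by Day 28 + 3 = 31, nominal Visit 5 is by Day 59, or Day 62 with the window, so it always has two labels. No sentence in the SAP says whether nominal visit or window prevails.

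That stands as a description of the text. The claim about Visit 4 is weaker. It needs treatment end date to mean last dose, against the schedules, the Visit 4/ET row and the ECG remark, and for the MSQ it also carries a note from the safety table over to another table. The consequences do not follow either. In a listing both MSQ records appear, so no rule for choosing one is needed. Week 4 and Week 8 count elapsed time from first dose and do not claim that the participant was on drug. The display rules may also sit in the separate specification document mentioned in SAP 1; that was not available and is not relied on here.

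**Conclusion.** No change is called for. The SAP leaves the end of the open-label period undefined, and its windows overlap for some early discontinuers. On either reading this affects a Visit 5 on or before Day 70, that is, a last dose by Day 42 when Visit 5 is 28 days later. The relabelling of Visit 4 arises only on the last-dose reading, which most of the surrounding text contradicts. An analyst would resolve both points in the obvious way: Visit 4 to Week 12, Visit 5 to Follow-up, early-termination records shown with their dates. The summary-table sentences in SAP 6.4.1 are a clerical carry-over that SAP 6.2 overrides for change summaries.

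The effect is confined to a visit label in a listing, for at most about 3 participants. The efficacy endpoint, adverse-event counts and flags for potentially clinically significant values stay the same under every reading. This rests on two assumptions: enrolment stays near 3, and the outputs remain listings as SAP 6.2 states. If by-visit or End of Treatment summaries were reinstated for a larger group, the period end and label precedence would need to be settled first.
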